6.2. Subgroup Analyses

The primary efficacy endpoint and some of the safety, PK and immunogenicity endpoints may be analyzed for the older (50-64 years old) and elderly (65-80 years old) separately in an exploratory fashion. Also, these endpoints may be listed and summarized for specific subjects of interest (e.g. renally impaired group).

6.3. Missing Data

For subjects with missing data on efficacy endpoints, no imputation will be used. For binary endpoints, the missing data will be excluded from the calculation of proportions.

For the purpose of determining inclusion of AEs in the treatment-emergent AE (TEAE) summary tables, incomplete or missing AE onset and end dates will be imputed as follows:

Incomplete or missing onset dates (where UK and UNK indicate unknown or missing day and month, respectively):

- UK-MMM-YYYY: If the month and year are different from the month and year of the first dose of study drug, assume 01-MMM-YYYY. If the month and year are the same as the first dose of study drug month and year, and the end date (after any imputation) is on or after the dose of study drug, then assume the date of the dose of study drug. If the month and year are the same as the dose of study drug month and year and the end date (after any imputation) is prior to the dose of study drug, then assume the end date for the onset date.
- DD-UNK-YYYY or UK-UNK-YYYY: If the year is different from the year of dose of study drug, assume DD-JAN-YYYY or 01-JAN-YYYY of the onset year, respectively. If

the year is the same as the dose of study drug year, and the end date (after any imputation) is on or after the dose of study drug, then assume the date of the dose of study drug for the onset date. If the year is the same as the dose of study drug, and the end date (after any imputation) is prior to the dose of study drug, then assume the end date for the onset date.

- Missing onset date: If the onset date is completely missing and the end date (after any imputation) is on or after the start of administration of study drug, then assume the onset date to be the start of administration of study drug. If the end date (after any imputation) is prior to the start of administration of study drug, then assume the end date to be the onset date.

Incomplete or missing end dates (where UK and UNK indicate unknown or missing day and month respectively):

- UK-MMM-YYYY: Assume the last day of the month;
- DD-UNK-YYYY or UK-UNK-YYYY: Assume DD-DEC-YYYY or 31-DEC-YYYY, respectively;
- Missing end date: Assume 31-DEC-YYYY, where YYYY is the year of the start of administration of study drug.

An AE with missing onset time but with an onset date the same as the start of administration date of study drug will be classified as treatment-emergent, unless the AE was reported pre-dose with the same or worse intensity or frequency.

Medications with missing start time but with a start date the same as the start of administration of study drug date will be considered as being taken on or after the initiation of study drug, unless the electronic case report form (eCRF) question “Was the medication/therapy taken prior to the study” is answered as “Yes” which is considered as being taken prior to the initiation of study drug.

Handling of missing PK data is specified in Section 9.5 and handling of PD data is specified in Section 9.6.

7. SUBJECT DISPOSITION

7.1. Disposition

Subject disposition will be presented for all screened subjects, including number of screen-failed subjects, number of subjects enrolled (i.e. receiving ticagrelor) and number of subjects randomized. For number of subjects randomized, subject disposition will be presented by randomized treatment group and total.

Number and percentage of subjects in the following categories will be summarized as appropriate:

- Screen failed
- Randomized (ITT Population)
- mITT Population
- Safety Population
- Per-Protocol Population
- PK Population

Additionally, a summary of study completion and treatment completion status will be presented along with reasons for discontinuation if any.

7.2. Protocol Deviations, Inclusion, and Exclusion Criteria

Protocol deviations will be presented in a data listing. Eligibility with regards to inclusion and exclusion criteria will be listed in a separate listing.

8. DEMOGRAPHIC AND BASELINE CHARACTERISTICS

8.1. Demographic and Baseline Characteristics

The demographic and baseline characteristics will be summarized with respect to sex, age (years), height (cm), weight (kg), BMI (kg/m^2), race, and ethnicity by treatment group. These summaries will be calculated for mITT, ITT and Safety Populations. Summary statistics include number of subjects with non-missing data, mean, standard deviation, median, minimum, and maximum for continuous variables, and number and percentage of patients in each category for categorical variables.

The counts and percentage of subjects who had been on aspirin before Day -7 or who initiated aspirin on Day -7 will be presented by treatment.

8.2. Medical History

Medical and surgical history and concomitant diseases will be coded according to the latest version of MedDRA and presented in listings.

8.3. Prior and Concomitant Medication

Prior medications are defined as medications taken prior to the initiation of study drug. Concomitant medications are defined as medications that were taken on or after the initiation of study drug. A medication can be considered as both prior and concomitant if the medication is taken prior to the initiation of study drug and continued into the treatment period.

Medications taken prior to ticagrelor, concomitant with ticagrelor and concomitant with the study treatments PB2452 and placebo will be presented separately.

Ticagrelor and aspirin, which will be received by all study subjects, are considered pre-treatments and will be excluded from the prior medication list.

Prior and concomitant medications will be coded using the latest version of the World Health Organization Drug Dictionary (WHO-DD).

9. EFFICACY

9.1. Analysis of Primary Efficacy Endpoint

All efficacy analyses will primarily be based on the mITT Population. Supportive analyses will be performed based on the ITT and Per-Protocol Population.

The primary endpoint is defined as the minimum % inhibition of PRU assessed by VerifyNow within 4 hours (inclusive) after the initiation of study drug. Percent inhibition of PRU is calculated as $100 * [(PRU_{bsl} - PRU_{trt})/PRU_{bsl}]$, where PRU_{bsl} refers to the PRU value measured before treatment with ticagrelor and PRU_{trt} refers to the PRU value measured posttreatment with the study drug.

Results by treatment groups will be summarized at baseline, at the timepoint where minimum is achieved (nadir), and percent inhibition from baseline using descriptive statistics: number of subjects with non-missing data, mean, standard deviation, median, minimum, and maximum. To complete the clinical picture, the % inhibition of PRU from baseline will be summarized at all time points using descriptive statistics.

Hypothesis testing will also be conducted using a 2-sided two-sample t-test test with a significance level of 0.05 to compare the efficacy of PB2452 and placebo. The corresponding 95% confidence interval will be provided for the mean difference between PB2452 and placebo.

In order to compare the response to the Phase 3 patient study which does not include a pre-ticagrelor baseline, percent inhibition of PRU will also be calculated as $100 * [(180 - PRU_{trt})/180]$, where PRU_{tttttt} refers to the PRU value measured at a given visit following start of study drug infusion. A PRU value of 180 is considered the lower limit of normal (LLN) platelet function, as described in the VerifyNow® P2Y₁₂ PRUTest® manufacturer's user guidance. This alternative calculation will be used to analyze the primary endpoint in an exploratory manner using the methods described above.

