9.3 Testing Procedures

9.3.1 Analysis of the Primary Efficacy Endpoint

All efficacy analyses will primarily be based on the mITT population.

The primary efficacy analysis compares the primary endpoint between PB2452 and placebo. The primary endpoint is defined as the minimum % inhibition of PRU assessed by VerifyNowTM PRUTestTM (VerifyNowTM, 2016) within 4 hours (inclusive) after the initiation of study drug. Percent inhibition of PRU is calculated as 100 * [(PRU_{bsl} – PRU_{trt})/PRU_{bsl}], where PRU_{bsl} refers to the PRU value measured before treatment with ticagrelor and PRU_{trt} refers to the PRU value measured posttreatment with the study drug.

Results by treatment groups will be summarized at baseline, at the timepoint where minimum is achieved, and percentage inhibition from baseline using descriptive statistics: N, mean, SD, median, minimum, and maximum. To complete the clinical picture, the % inhibition of PRU from baseline will be summarized at all time points using descriptive statistics.

Hypothesis testing will also be conducted as a 2-sided test with a significance level of 0.05 to compare the efficacy of PB2452 and placebo. Assuming that the population median minimum % inhibition of PRU are expressed as μ_{PB2452} and $\mu_{Placebo}$ for the PB2452 and placebo groups, respectively, the treatment comparison to be tested is $\Delta = \mu_{PB2452} - \mu_{placebo}$. The null (H₀) and alternative (H₁) hypotheses for each comparison are:

$$H_0: \Delta = 0 \quad \text{vs.} \quad H_1: \Delta \neq 0$$

This test will be conducted using an exact Wilcoxon rank-sum test. The hypothesis test for the primary endpoint will be performed at 2-sided $\alpha = 0.05$. The Hodges-Lehman estimate of location shift and a 95% Hodges-Lehman confidence interval will be constructed on the difference in between PB2452 and placebo.

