- g ASA 81 mg will be taken on Days -7, -6, -5, -4, -3, -2, -1, and on Day 1 (2 hours before study drug is started). Subjects who enter the study already taking ASA daily must document a daily ASA 81 mg dose between Day -7 and Day -3. Patients will receive daily ASA 81 mg between Day -3 (or Day -2 if the patient took ASA 81mg on Day -3 prior to Check-in) and Day 1 at the clinical facility and will suspend further ASA dosing until discharge from the clinical facility.
- h Beginning in the morning on Day -2, a single dose of oral ticagrelor 180 mg will be given, followed by oral ticagrelor 90 mg every 12 hours for 4 additional doses through to Day 1 (2 hours before study drug is initiated; this will be 5 total doses of ticagrelor).
- i PB2452/placebo will be administered at Hour 0 of Day 1.
- j Blood samples for determination of plasma PB2452, plasma ticagrelor/TAM and unbound plasma ticagrelor/TAM will be collected within 10 minutes prior to the initiation of PB2452/placebo infusion (Hour 0) and at 5, 10, 30 minutes and 1, 2, 4, 8, 12, 20, 24, 36, and 48 hours after initiation of study drug infusion. And on days -2, 1, 2, 3, 7, and 35 ± 3 after initiation of study drug infusion.
- k Blood samples for PD analysis (PRU/VASP testing) will be collected at the following timepoints: Day -2 (up to 60 minutes prior to first ticagrelor dose) and Hour 0 (up to 10 minutes prior to PB2452/placebo infusion), 5, 10, 30 minutes, 1, 2, 4, 8, 12, 20, 24, 36 and 48 hours after initiation of PB2452/placebo infusion.
- If there is sufficient material leftover from PK and/or PD blood samples, additional platelet function-related biomarkers, such as P-selectin, will be tested to support hypothesis generation for future studies.
- l Subjects may be required to return to the site for collection of additional follow-up samples, if the sample collected at Day 35 ± 3 tests positive for treatment-emergent ADAs. These visits may occur approximately 3 months after the final study visit and approximately every 6 months thereafter or until antibody levels return to baseline level.
- m Infusion site assessments will be performed for all subjects within 15 minutes before initiation of PB2452/placebo infusion at Hour 0, 1, 3, 24, and 48 hours after initiation of PB2452/placebo infusion, and on Day 7.

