4.2. Sample Size Justification

Approximately 200 subjects 50-80 years old inclusive will be enrolled across US or, if needed, other countries at 5-15 sites. The subjects will be randomized in a 3:1 ratio receiving either the

PB2452 investigational study drug or placebo. Hence, a total of approximately 150 subjects will be receiving PB2452 and approximately 50 subjects will be receiving placebo.

The primary efficacy endpoint will be assessed by comparing the minimum % inhibition of PRU assessed by VerifyNow within 4 hours after the initiation of study drug between PB2452 group vs placebo group. A sample size of approximately 200 subjects with 3:1 allocation ratio (PB2452:placebo) will provide > 99% power to detect a mean difference of 15 in % inhibition of PRU between PB2452 and placebo group using a two-sided two-sample t-test with type I error of 0.05 (a standard deviation of 20 for % inhibition is assumed within each treatment group, which is obtained from previous studies). The sample size of 200 (150 active vs 50 placebo) will provide substantial safety information on PB2452 in older and elderly healthy subjects.

Subjects who withdraw from the study and who do not have adequate collection of safety, hemodynamic and pharmacokinetic samples for evaluation of safety, PK, and PD profiles may be replaced at the discretion of the Sponsor. Any replacement subject will be assigned to receive the same treatment as the subject he or she is replacing.

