6. GENERAL ASPECTS OF THE STATISTICAL ANALYSIS

6.1. Key Definitions

The Study Day is the day relative to the date of treatment (Day 1). In other words,

$$\text{Study Day} = \text{Date} - \text{Date of treatment} + 1,$$

if Date is on or after Date of treatment; or

$$\text{Study Day} = \text{Date} - \text{Date of treatment},$$

if Date is before Date of dosing.

For efficacy endpoints, baseline values will be defined as the last value before ticagrelor is administered, which is expected to be on Day -2. The pre-treatment value is defined as the last value before study drug is administered, which is expected to be on Day 1 (up to 10 minutes prior to PB2452/placebo infusion). If Day 1 value is missing, the value prior to that will be used as pre-treatment.

For all other endpoints, unless otherwise specified, baseline is the last non-missing observation before exposure to study treatment PB2452 or placebo, which is expected to be the pre-study drug measurement on Day 1, or Screening if the Day 1 data are not available.

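### The primary comparison of minimum % inhibition of PRU leaves out the Hour 0 PRU collected in every subject; a prespecified adjusted analysis would tighten the reported estimate at no data cost

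*SAP*

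**What the plan says.** SAP 9.1 tests the primary endpoint "using a 2-sided two-sample t-test test with a significance level of 0.05 to compare the efficacy of PB2452 and placebo" and gives a 95% CI for the mean difference. Protocol 9.3.1 says "This test will be conducted using an exact Wilcoxon rank-sum test", with a Hodges-Lehmann estimate and interval. Neither section names a covariate, and neither document plans an adjusted sensitivity analysis.

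Two PRU values precede the infusion. The footnotes to the SAP schedule (section 4.1) place them at "Day -2 (up to 60 minutes prior to first ticagrelor dose) and Hour 0 (up to 10 minutes prior to PB2452/placebo infusion"). The Day -2 value is the efficacy baseline and the denominator of % inhibition. SAP 6.1 deals with the later one: "The pre-treatment value is defined as the last value before study drug is administered", expected on Day 1. That value enters percent reversal in SAP 9.2, but not the primary comparison.

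SAP 4.2 states that the design "will provide > 99% power to detect a mean difference of 15 in % inhibition of" PRU, based on a "two-sided two-sample t-test with type I error of 0.05", where "a standard deviation of 20 for % inhibition is assumed within each treatment group, which is obtained from previous studies". Protocol 7.2.2 specifies simple randomization without stratification.

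**The concern.** Dividing by Day -2 PRU removes differences in native platelet reactivity. It does not remove differences in how strongly ticagrelor has inhibited each subject by Hour 0. A placebo subject's minimum over the next 4 hours should largely follow that Hour 0 level, because the infusion starts near peak ticagrelor concentration (protocol 2.1.2.1). This is inference; the documents report no correlation. Some spread at Hour 0 is plausible: subjects on moderate or strong CYP3A inhibitors may enter (protocol 4.1), and protocol 2.1.2.2 links moderate inhibitors to higher ticagrelor levels.

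The stake is the estimate. The SAP reports a mean difference with an interval, and that interval may be wider than the collected data require. With about 50 placebo subjects and no stratification, the arms may also differ by chance at Hour 0, and no planned analysis would show whether that mattered.

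**Working it through.** **Inputs.** Difference 15, SD 20 per arm, 150 versus 50, two-sided alpha 0.05 (SAP 4.2). The correlation ρ between Hour 0 inhibition and the endpoint is not in the documents; 0.3 to 0.7 is an assumed range.

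**The plan's own figure.** SE = 20 × √(1/150 + 1/50) = 3.266. Power is 99.6% by the normal approximation and 99.5% by the noncentral t with 198 df. The stated figure of more than 99% reproduces.

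**Unadjusted precision.** Half-width = t(0.975; 198) × SE = 1.972 × 3.266 = 6.44 points.

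**Case A: same correlation in both arms.** Variance is multiplied by 1 − ρ².

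**Case B: correlation in placebo only, common slope.** The pooled slope is ρ/4 in SD units, because placebo is a quarter of the sample. Per-arm residual variances, as multiples of 400, are 1 + ρ²/16 (active) and 1 − ρ²/2 + ρ²/16 (placebo). Dividing by 150 and 50, adding, and comparing with the unadjusted sum gives a factor of 1 − 0.3125ρ².

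**Case C: correlation in placebo only, with a treatment-by-centred-covariate term.** The variance is 400 × [(1 − ρ²)/50 + 1/150 + ρ²/200], where the last term is the sampling variation of the pooled covariate mean. The large-sample factor is 1 − 0.5625ρ².

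| Assumed ρ | A: half-width | B: half-width | C: variance reduction |
|---|---|---|---|
| 0.3 | 6.14 | 6.35 | 5% |
| 0.5 | 5.58 | 6.18 | 14% (about 13% after the cost of estimating slopes) |
| 0.7 | 4.60 | 5.93 | 28% |

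In Case C the half-width is about 6.0 at ρ = 0.5 (6.44 × √0.87) and 5.5 at ρ = 0.7 (6.44 × √0.72). At ρ = 0.1 in both arms the half-width is 6.41, practically no gain.

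**Effect on power.** In Case A, t-test power rises from 99.5% to 99.8% at ρ = 0.3 and 99.95% at ρ = 0.5. The gain cannot exceed half a percentage point.

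**Chance imbalance.** The difference between arms in mean Hour 0 value has SD √(1/150 + 1/50) = 0.163 covariate SDs. An imbalance above 0.25 SD in either direction has z = 0.25/0.163 = 1.53, a probability of about 13%. At a common ρ of 0.5, an imbalance of 0.25 SD moves the unadjusted difference by 0.25 × 0.5 × 20 = 2.5 points.

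**The case against.** The strongest objection is that the gain is small and no decision depends on it. The t-test is valid under randomization, its interval already allows for chance imbalance, and power is near its ceiling. Against a planned difference of 15, a half-width of 6.2 instead of 6.4 changes no conclusion. All of that stands, and it makes this an efficiency point.

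A reader might take the narrowest interval, 4.60 points, as the precision being lost. The documents do not support that. It needs a correlation of 0.7 in both arms, while protocol 2.1.4 reports that PB2452 brought platelet activity back to roughly baseline in Phase 1. If reversal is nearly complete, Hour 0 inhibition may predict little in the active arm, and the placebo-only figures are the more realistic guide. Starting every infusion near peak ticagrelor concentration may also narrow the Hour 0 spread. Some gain can still remain: at equal SDs the placebo arm supplies (1/50)/(1/50 + 1/150) = 75% of the variance of the difference, and it is the arm where Hour 0 should predict.

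A reader might also infer that the plan ignores its pre-infusion data. It does not. Day -2 PRU is in the endpoint, and percent reversal of PRU, listed second in the SAP 9.2 hierarchy, contains the Hour 0 value. But percent reversal is a different endpoint; it does not sharpen the primary estimate.

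Finally, ANCOVA could become a third candidate primary method while the SAP's t-test on means and the protocol's Wilcoxon test on medians still conflict. That is fair: adjustment should be settled together with that conflict.

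**Conclusion.** The point holds as an inexpensive improvement in precision. Both documents leave the primary comparison unadjusted for a pre-infusion value that they schedule in every subject. The possible benefit is a narrower interval for the mean difference and an adjusted estimate if the arms differ at Hour 0. At an assumed correlation of 0.5, the half-width of 6.44 becomes 5.58 if the correlation holds in both arms. If it holds in placebo only, it becomes about 6.2 with a common slope or about 6.0 with an interaction term.

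These sizes rest on the plan's SD of 20, full arms of 150 and 50, and correlations that the documents do not give. Nothing here suggests that the trial is underpowered, that the planned test is biased, or that the primary objective is at risk.

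**What to change.** When the SAP t-test and the protocol Wilcoxon test are reconciled, and before unblinding, add to SAP 9.1:

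- **Model.** ANCOVA of minimum % inhibition of PRU on treatment, centred Hour 0 % inhibition and their interaction, with heteroscedasticity-robust standard errors. Day -2 PRU is an optional further covariate. If slopes differ by arm, the standard error should also include the variation of the pooled covariate mean (the ρ²/200 term in Case C), which the usual robust formula omits.
- **Reporting.** Give the adjusted mean difference and 95% CI, with the unadjusted t-test or the rank test as a check.
- **Missing Hour 0 covariate.** Use the pooled mean over both arms. Do not reuse the SAP 6.1 fallback to the preceding value: on the SAP schedule that is the pre-ticagrelor sample, so the covariate would be 100 × (PRUbsl − PRUbsl)/PRUbsl = 0% inhibition.
- **Continuous secondary endpoints.** Use the Hour 0 PRI covariate for minimum % inhibition of PRI and for PRI AUC, and the Hour 0 PRU covariate for PRU AUC. Leave percent reversal unadjusted, since it already contains the Hour 0 value.

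The cost is SAP text and a little programming. No new data are needed.

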9.2. Analysis of Secondary Efficacy Endpoints

The secondary efficacy analysis compares a number of secondary endpoints between the two treatment groups. The secondary endpoints below will be formally evaluated if the primary efficacy hypothesis was supported. A hierarchical approach will be used to control for multiplicity. The secondary endpoints will be tested in the order presented below. There are three types of endpoints:

Continuous endpoints:

- Minimum %inhibition of PRI assessed by VASP within 4 hours after the initiation of study drug. %inhibition of PRI is calculated as $100 * [(PRI_{bsl} - PRI_{trt})/PRI_{bsl}]$. PRI_{bsl} refers to the PRI value measured before treatment with ticagrelor and PRI_{trt} refers to the PRI value measured posttreatment with the study drug.
- Percent reversal of PRU within 4 hours after the initiation of study drug. Percent reversal is calculated as $100 * [(PRU_{trt} - PRU_{pre-trt})/(PRU_{bsl} - PRU_{pre-trt})]$. $PRU_{pre-trt}$ is the PRU value prior to administration of study drug.

- Percent reversal of PRI within 4 hours after the initiation of study drug. Percent reversal is calculated as $100 * [(PRI_{trt} - PRI_{pre-trt}) / (PRI_{bsl} - PRI_{pre-trt})]$. $PRI_{pre-trt}$ is the PRI value prior to administration of study drug.
- PRU AUC for the first 4 hours.
- PRI AUC for the first 4 hours.

The continuous endpoints will be compared between the two treatment groups using a two-sample t-test, as used for the primary endpoint.

Binary endpoints:

- Proportion of patients with normalized platelet reactivity units within 4 hours after the initiation of study drug. Normalized platelet reactivity is defined as $PRU \geq 180$.
- Proportion of patients with $\geq 60\%$, $\geq 80\%$, and 100% of PRU response rate within 4 hours after the initiation of study drug. A PRU response is defined as the $100 * (PRU_{trt}/PRU_{bsl})$.
- Proportion of patients with $\geq 60\%$, $\geq 80\%$, and 100% of PRI response rate within 4 hours after the initiation of study drug. A PRI response is defined as the $100 * (PRI_{trt}/PRI_{bsl})$.

Number and percent of patients achieving normalized PRU, or 60%, 80%, 90% and 100% of baseline platelet aggregation, and with normalized platelet activity will be summarized by timepoint and treatment. A similar analysis will be done for proportion of patients with $\geq 60\%$, $\geq 80\%$, 90% and 100% of PRI response rate.

The dichotomous secondary endpoints will be compared between the treatment groups using Fisher's Exact test at two-sided 5% significance level.

9.3. Other Efficacy Endpoints:

The following PD parameters may be calculated and summarized using %baseline/actual PRU data from the VerifyNow assay. The maximal endpoints will be presented as other continuous endpoints using summary statistics. The median time-to-event endpoints will be summarized using the Kaplan Meier method. Time will be censored if the event is not attained before the study end.

APRUMax	Maximal actual PRU
APRUMax4h	Maximal actual PRU within 4 h
PRUmax	Maximal percent of baseline PRU
TPRUMax	Time to maximal actual PRU
TPRU180	Time to 180 or higher actual PRU, calculated as the first observed time point (no extrapolation) when the actual PRU reaches 180 or above
TPRU200	Time to 200 or higher actual PRU, calculated as the first observed time point (no extrapolation) when the actual PRU reaches 200 or above

TPRU220	Time to 220 or higher actual PRU, calculated as the first observed time point (no extrapolation) when the actual PRU reaches 220 or above
TPRU60%	Time to 60% of baseline PRU, calculated as the first observed time point (no extrapolation) when %baseline PRU reaches 60% or above
TPRU80%	Time to 80% of baseline PRU, calculated as the first observed time point (no extrapolation) when %baseline PRU reaches 80% or above
TPRU100%	Time to 100% of baseline PRU, calculated as the first observed time point (no extrapolation) when %baseline PRU reaches 100%

Similar parameters may also be reported for PRI.

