- Total amount of drug excreted in urine at 24 hours (Ae₂₄) and at 48 hours (Ae₄₈)
- ae from time t1 to t2 hours including 0 to 6, 6 to 12, 12 to 24 and 24 to 48 hours (Aet1-t2)
- Fraction excreted in urine from 1 to 24 hours (Fe₂₄) and from 1 to 48 hours (Fe₄₈)
- Renal clearance (CLr) for 24 hours

- 3. Additional reversal endpoints:
 - Minimum %inhibition of PRI assessed by VASP within 4 hours after the initiation of study drug. %inhibition of PRI is calculated as 100 * [(PRI_{bsl} – PRI_{trt})/PRI_{bsl}]. PRI_{bsl} refers to the PRI value measured before treatment with ticagrelor and PRI_{trt} refers to the PRI value measured posttreatment with the study drug
 - PRU AUC for the first 4 hours
 - Proportion of subjects with normalized platelet reactivity units within 4 hours after the initiation of study drug Normalized platelet reactivity is defined as $PRU \ge 180$.
 - Proportion of subjects with ≥60%, ≥80%, and 100% of PRU response rate within 4 hours after the initiation of study drug. A PRU response is defined as the 100 *(PRU_{trt}/PRU_{bsl})
 - Time to 60%, 80%, 100% of PRU response rate within 4 hours after the initiation of study drug
 - Duration of 80% and 100% response rate by PRU
 - PRI AUC for the first 4 hours
 - Proportion of subjects with ≥60%, ≥80%, and 100% of PRI response rate within 4 hours after the initiation of study drug. A PRI response is defined as the 100 * (PRI_{trt}/PRI_{bsl})
 - Time to 60%, 80%, 100% PRI response rate within 4 hours after the initiation of study drug
 - Duration of 80% and 100% response rate by PRI
 - Percent reversal of PRU within 4 hours after the initiation of study drug. Percent reversal is calculated as 100 *[(PRU_{trt} PRU_{pre-trt})/(PRU_{bsl} PRU_{pre-reversal})]. PRU_{pre-trt} is defined as the PRU value prior to administration of study drug
 - Percent reversal of PRI within 4 hours after the initiation of study drug. Percent reversal is calculated as 100 * [(PRI_{trt} PRI_{pre-trt})/(PRI_{bsl} PRI_{pre-trt})]. PRI_{pre-reversal} is defined as the PRU value prior to administration of study drug

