- Total amount of drug excreted in urine at 24 hours (Ae_{24}) and at 48 hours (Ae_{48})
- AE from time t_1 to t_2 hours including 0 to 6, 6 to 12, 12 to 24 and 24 to 48 hours (Ae_{t1-t2})
- Fraction excreted in urine from 1 to 24 hours (Fe_{24}) and from 1 to 48 hours (Fe_{48})
- Renal clearance (CLr) for 24 hours.

Additional Reversal Endpoints

- Minimum %inhibition of PRI assessed by VASP within 4 hours after the initiation of study drug. %inhibition of PRI is calculated as $100 * [(PRI_{bsl} - PRI_{trt})/PRI_{bsl}]$. PRI_{bsl} refers to the PRI value measured before treatment with ticagrelor and PRI_{trt} refers to the PRI value measured posttreatment with the study drug.
- PRU AUC for the first 4 hours.
- Proportion of patients with normalized platelet reactivity units at any time within 4 hours after the initiation of study drug. Normalized platelet reactivity is defined as $PRU \geq 180$.
- Proportion of patients with $\geq 60\%$, $\geq 80\%$, and 100% of PRU response rate at any time within 4 hours after the initiation of study drug. A PRU response is defined as the $100 * (PRU_{trt}/PRU_{bsl})$.
- Time to 60% , 80% , 100% of PRU response rate within 4 hours after the initiation of study drug.
- Duration of 80% and 100% response rate by PRU.
- PRI AUC for the first 4 hours.
- Proportion of patients with $\geq 60\%$, $\geq 80\%$, and 100% of PRI response rate within 4 hours after the initiation of study drug. A PRI response is defined as the $100 * (PRI_{trt}/PRI_{bsl})$.
- Time to 60% , 80% , 100% PRI response rate within 4 hours after the initiation of study drug
- Duration of 80% and 100% response rate by PRI
- Maximum percent reversal of PRU within 4 hours after the initiation of study drug. Percent reversal is calculated as $100 * [(PRU_{trt} - PRU_{pre-trt})/ (PRU_{bsl} - PRU_{pre-trt})]$. $PRU_{pre-trt}$ is defined as the PRU value prior to administration of study drug.
- Maximum percent reversal of PRI within 4 hours after the initiation of study drug. Percent reversal is calculated as $100 * [(PRI_{trt} - PRI_{pre-trt})/ (PRI_{bsl} - PRI_{pre-trt})]$. $PRI_{pre-trt}$ is defined as the PRI value prior to administration of study drug.

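### The time-to-response endpoints stop at 4 hours, but the only SAP analysis of them has no 4-hour limit and runs to study end

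*SAP*

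**What the plan says.** **The endpoint.** Protocol 3.2.2 lists, among the additional reversal endpoints, "Time to 60%, 80%, 100% of PRU response rate within 4 hours after the initiation of study drug". It has a parallel item for PRI. SAP 3.2 carries the same limit ("of PRU response rate within 4 hours after the initiation of study drug") and also repeats the PRI item.

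**The analysis.** SAP 9.2 says there are three types of secondary endpoint, to be tested in a fixed order, and then lists only continuous and binary ones. Times to response appear only in SAP 9.3, among the other efficacy endpoints. That section is optional: "The following PD parameters may be calculated and summarized using %baseline/actual PRU data from the VerifyNow assay". A representative definition is "Time to 60% of baseline PRU, calculated as the first observed time point (no extrapolation) when %baseline PRU reaches 60% or above"; the 80% and 100% versions are parallel, and similar PRI parameters may be reported. None has a 4-hour limit. The method is stated as "The median time-to-event endpoints will be summarized using the Kaplan Meier method", with the rule "Time will be censored if the event is not attained before the study end".

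**The measurements.** Footnote k of SAP Table 1 schedules PRU/VASP samples at "5, 10, 30 minutes, 1, 2, 4, 8, 12, 20, 24, 36 and 48 hours after initiation of PB2452/placebo infusion". None is scheduled on Day 7 or Day 35.

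**Study end.** SAP 9.3 does not define the term. SAP 13 reports the Day 35 visit as end of study, and Protocol 6.1.7 says the trial concludes at that visit. Protocol 6.3 also gives a trial-level definition, the last subject's last visit.

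**The concern.** The endpoint list asks how fast subjects respond in a 4-hour window. The analysis section measures first response over the whole PRU profile. Protocol 4.2 expects placebo subjects to regain platelet function as ticagrelor falls. Without the window, such recovery at the 8- to 48-hour samples is an event, so a table labelled as the 4-hour secondary endpoint could show a placebo wash-out time.

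This matters because speed is part of the stated hypothesis (rapid and sustained reversal) and these times are prespecified secondary endpoints. Two programmers could also produce different medians, one following SAP 3.2 and the other SAP 9.3.

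A smaller problem sits in the same sentence. Kaplan-Meier needs each event-free subject to be censored when event status was last known. Study end is later than any PRU reading.

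**Working it through.** **No planned figure for this point.** The documents state no expected time to response. Their one design figure, power above 99% for the primary endpoint, reproduces: SE = 20 × √(1/150 + 1/50) = 3.27; 15/3.27 = 4.59; Φ(4.59 − 1.96) = 0.996. Nothing below depends on it.

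**Step 1: three time limits.**

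| Limit | Source | Hours from start of study drug |
|---|---|---|
| Endpoint window | Protocol 3.2.2, SAP 3.2 | 4 |
| Last scheduled PRU/VASP | SAP Table 1, footnote k | 48 |
| Study end, read as Day 35 | SAP 13, Protocol 6.1.7 | (35 − 1) × 24 = 816 |

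The ±3-day window makes the last figure 744 to 888 hours. Day 35 is 816/48 = 17 times the last PRU time and 816/4 = 204 times the endpoint window.

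**Step 2: effect of dropping the 4-hour limit.** The documents give no placebo recovery distribution, so this step rests on assumptions: 50 placebo subjects, log-normal time to the threshold with log-SD 0.6, true median m, complete sampling, and response recorded at the next scheduled sample. The expected fraction responding by time h is Φ(ln(h/m)/0.6). For m = 24:

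- h = 4: Φ(−2.99) = 0.001, or 0 of 50.
- h = 48: Φ(1.16) = 0.876, or 44 of 50.

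| Assumed true median (h) | Events by 4 h | Median, 4-h limit | Events, run to study end | Median, run to study end |
|---|---|---|---|---|
| 12 | 2 | not reached | 49 | 12 h |
| 24 | 0 | not reached | 44 | 24 h |
| 36 | 0 | not reached | 34 | 36 h |
| 60 | 0 | not reached | 18 | not reached |

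The sizes depend on the assumptions. The direction does not: any first response after 4 hours is an event under SAP 9.3 and not under SAP 3.2.

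**Step 3: effect of Day 35 against 48 hours.** With complete sampling, censoring at 48 hours and at 816 hours gives identical events and medians in every row above. The two differ only if a subject's PRU readings stop early and that subject is kept at risk, event-free, to study end. Suppose a fraction f has no PRU after 4 hours, unrelated to outcome, and the true median is 24 hours. Censoring at the last PRU estimates response by 24 hours at about 0.50. Keeping those subjects at risk gives about (1 − f) × 0.50: 0.45, 0.40 and 0.35 for f = 10%, 20% and 30%. In simulated trials of 50 the typical Kaplan-Meier median moves from 24 to 36 hours. The documents give no value for f.

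**Step 4: can other text supply the limit?** SAP 9.2 does not contain the missing type. SAP 6.3 sends PD missing-data handling to a Section 9.6, but the efficacy section ends at 9.3. SAP 9.3 lists maximal PRU both overall and within 4 hours, so a 4-hour limit is marked there when it is meant. It cannot be read into the 60/80/100% times.

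**The case against.** The best defence is that SAP 9.3 describes whole-profile PD parameters and never claims to analyse the 4-hour endpoints. It is optional, its 180/200/220 PRU times have no 4-hour definition anywhere, and it separates 4-hour from overall maxima. This is a fair reading, but it moves the gap without closing it: the 4-hour times then have no analysis at all, because SAP 9.2 omits them.

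Second, a Kaplan-Meier curve up to 4 hours does not depend on later events, so the 4-hour result can be read from the longer curve. That is true with complete early sampling. The SAP, however, promises a median, and the placebo median is the figure that changes.

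Third, showing placebo recovery is a purpose of the control arm under Protocol 4.2. A 48-hour summary is therefore legitimate, provided it does not carry the 4-hour endpoint's name.

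Fourth, a reader might infer that the SAP fixes Day 35 as the censoring time and so biases the curve generally towards non-response. The text does not support that. It says when a time is censored, not at what time, and leaves study end undefined. SAP 6.3 rules out imputation for missing efficacy data, and SAP 9.3 uses first observed times without extrapolation. Subjects are in clinic for the 48 hours of sampling, so early loss of readings should be uncommon. What stands is that the censoring time is unspecified and that the natural reading places it after the last measurement.

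**Conclusion.** The mismatch is real. Secondary endpoints defined over 4 hours have no matching analysis, and the nearest one would count placebo wash-out recovery as response. The placebo median can change from not reached by 4 hours to a recovery time: 12 to 36 hours if true medians in that range are assumed, and still not reached at an assumed 60 hours.

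The PB2452 median is probably unaffected. Protocol 2.1.2.2 and 2.1.4 describe reversal by 5 minutes in Phase 1, although they give no times by threshold.

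A reader might also infer a threat to the efficacy conclusion. There is none: these summaries are descriptive and outside the listed hierarchy, and the primary endpoint has its own analysis. The inconsistency does not extend to the times to 180, 200 and 220 PRU, which have no 4-hour definition.

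The gap between 48 hours and Day 35 is secondary. It biases the curve only through subjects whose sampling stops early, and its size cannot be derived from the documents; the range in Step 3 is illustrative.

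**What to change.** Three edits to the SAP before database lock:

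1. In 9.2, add the time-to-event type: time to 60%, 80% and 100% PRU and PRI response in the first 4 hours. Say whether it is descriptive or where it falls in the testing order, since 9.2 tests endpoints in the order listed.
2. For these times only, state: *a subject without the event is censored at the last evaluable PRU (PRI) assessment at or before 4 hours.*
3. In 9.3, for the times to 180, 200 and 220 PRU and for any 48-hour version of the 60/80/100% times (labelled exploratory), replace censoring by reference to study end with censoring at the last evaluable PRU (PRI) assessment.

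A single 4-hour rule for all of 9.3 would go too far, because it would truncate the 180/200/220 times as well. The cost is a few sentences and a small programming change. No new data, visits or subjects are needed, and the sample size is unaffected.
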